4.10 STUDY PROTOCOL

4.10.1 Randomisation method and allocation concealment

After receiving the ethical clearance from USM's Ethics Committee, the patient recruitment for this trial commenced. The study subjects were firstly screened against the eligibility criteria and those who met the criteria, informed consents were acquired from each one of them.

The study participants were then block-randomized using a block size of 4 with a balanced 1:1 allotment ratio without any covariate stratification. This method of randomization, instead of the simple randomization technique, was utilized to ensure that the number of study participants is equal in both intervention groups. In this case, for every block of four study participants, each two of them will be allotted to one intervention arm. The block randomization was performed using permuted block design, with the random numbers generated by a random number generator package in Stata 9.0 (StataCorp, College Station, Texas). This randomization process was performed by an

independent third-party statistician ([name] [name], Graduate Statistician (GradStat), the Royal Statistical Society, UK).

To ensure selection bias was prevented, the allocation sequence was kept inside a password-protected STATA 9.0 file which was only accessible to the independent third-party statistician. The sequence of treatment allotment was only revealed after a study participant was properly recruited and subsequently randomized to treatment allotment. To prevent ascertainment and performance bias, the study participants and the independent assessors (2nd medical officer) were shielded from the knowledge of the type of intervention received. However, the intervention was administered by the primary investigator (VG) who was not blinded to the kind of intervention received.

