4.1 STUDY DESIGN

A prospective, single center, two-parallel group, single (observer)-blinded controlled trial involving surgical patients undergoing upper limb surgeries at the HUSM surgical theatres.

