4.6 SAMPLING METHOD

Despite sufficient potential subjects for their recruitment into this trial, convenient sampling had to be used due to the time constraint imposed by the urgency for thesis submission within the tight submission window (early November).

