4.10.2 Details of the administered interventions

The premedication was first prescribed in the morning of the surgery. Upon arrival in the OT, all patients were monitored based on the standard anaesthesia monitoring and for relevant clinical parameters (baseline blood pressure (BP), saturation pressure of oxygen (spO₂), electrocardiography (ECG) and heart rate (HR)) which were obtained using the electric B30 monitor (Stimuplex D® plus 50mm, B. Braun, Melsungen, Germany) and documented before the BPB commenced. Subsequently, IV access of at least 20 G size was inserted on the selected hand of study participants.

Intravenous (IV) loading of Ringer's Lactate solution (B. Braun, Melsungen, Germany) 10 ml/kg was administered before performing the block. Brachial plexus block (BPB) was performed in the block corner at the recovery bay. Drugs regime and other standard equipment for BPB was prepared and acquired and these include:

- 5 mls of Lignocaine 2% for skin infiltration
- 20 mls of Ropivacaine (Naropin®, Astrazeneca) 0.75% + 20mg
 Parecoxib (Dynastat®, Pfizer)(1 mls) ---Group A

- 20mls Ropivacaine 0.75% + 1 ml Normal Saline----Group B.
- Ultra Sonographic machine (Mindray® Version M5, Mindray, Shenzen, China) with high frequency (10-15MHz) linear probe
- 50 to 80mm 22 G insulated peripheral nerve block needle. Vygon,
 France
- o 2% chlorhexidine in 70% isopropyl alcohol solution for skin cleaning

The BPB was implemented by a single operator and assessed by the independent 2nd medical officer in-charge who was blinded and oblivious to the treatment administered. No peripheral nerve stimulator was employed during the procedure. The detailed descriptions of the techniques utilized in the BPB are as follows:

- The block site will be cleaned and draped. The US probe also was draped for the procedure as well.
- SCB technique:
 - Subjects were positioned semi-recumbent with the head turned to the contralateral side with the ipsilateral shoulder slightly elevated with the pillow.
 - An exploratory scan was performed in all patients before the block, by positioning the probe on a coronal oblique plane above the clavicle.
 - Hypoechoic and pulsating supraclavicular artery was then identified, which was lying above the hyper echoic first rib. While maintaining the view of the artery, the probe was then angled until both the first rib and the pleura were also seen simultaneously.

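### A constant block of 4 with one unblinded operator leaves the end of each block deducible, so holding the list with a statistician does not by itself rule out selection bias

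*Combined protocol and SAP*

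**What the plan says.** Section 4.10.1 states that participants were "block-randomized using a block size of 4 with a balanced 1:1 allotment ratio without any covariate stratification". It spells out the composition: "for every block of four study participants, each two of them will be allotted to one intervention arm". Section 4.1 describes "A prospective, single center, two-parallel group, single (observer)-blinded controlled trial", so there is one running sequence.

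Section 4.10.2 says "The BPB was implemented by a single operator". Section 4.10.1 says "the intervention was administered by the primary investigator", "who was not blinded to the kind of intervention received".

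The stated safeguard is that "the allocation sequence was kept inside a password-protected STATA 9.0 file", open only to an independent statistician, with each assignment disclosed after the participant had been recruited. The section presents this as the means of preventing selection bias. Participants and the outcome assessor were blinded.

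On recruitment, section 4.6 says "convenient sampling had to be used due to the time constraint". Section 4.10.1 describes screening and consent without naming who did them. Nowhere do the documents say whether the block size was withheld from the operator.

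**The concern.** Locking the file hides the list. It does not hide the next assignment from someone who knows the block size and has personally given every earlier treatment in the same sequence. Once one arm has had its two places in a block, the rest of that block is determined.

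Blinding the participants and the assessor protects the outcome measurement. It does not protect the decision about whom to enrol next. If a predictable assignment coincided with discretion over enrolment, the arms could differ in prognosis from the start. Some discretion is conceivable: sampling was by convenience, and one inclusion criterion (section 4.8.1) is a judgement of how long surgery is expected to last. The tests in section 4.13 are unadjusted two-group comparisons, so the analysis would not correct such a difference. The limitations in section 6.4 do not mention predictability.

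**Working it through.** The plan gives no figure for predictability, so there is none to reproduce. The calculation below is for an observer who knows the block size and sees all past allocations.

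**Inputs.** Block size 4, two per arm, no strata (4.10.1); one centre (4.1); one unblinded operator (4.10.1, 4.10.2); 86 patients, 43 per arm (5.1).

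**One block.** Two A and two B can be ordered in 4!/(2!·2!) = 6 equally likely ways. An assignment is certain when one arm's two places are already used.

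| Position | Chance it is certain | Chance the best guess is right |
|---|---|---|
| 1 | 0 | 1/2 |
| 2 | 0 | 2/3 |
| 3 | 1/3 (the first two were alike) | 1/3 × 1 + 2/3 × 1/2 = 2/3 |
| 4 | 1 | 1 |
| Sum | 4/3 | 17/6 |

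Per assignment, the certain share is (4/3)/4 = 1/3 = 33.3%. The best-guess rate is (17/6)/4 = 17/24 = 70.8%. Under simple randomisation these would be 0% and 50%.

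**86 patients.** 86 = 21 × 4 + 2, that is, 21 full blocks and two patients in an incomplete block, neither of whom can be certain.

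- Expected number certain: 21 × 4/3 = 28, and 28/86 = 32.6%.
- Spread: each full block contributes 1 (probability 2/3) or 2 (probability 1/3), a variance of 2/9. The SD is √(21 × 2/9) = 2.2, and the possible range is 21 to 42.
- Best guess: 21 × 17/6 + 1/2 + 2/3 = 60.7 correct, and 60.7/86 = 70.5%.

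**Alternative schemes.** The fixed sizes are exact for full blocks. The varied sizes were simulated with 86 patients and 3,000 runs each, sizes equally likely, and an observer who knows the set of sizes but not their order.

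| Scheme | Certain beforehand | Best guess right |
|---|---|---|
| Fixed 4 | 33.3% | 70.8% |
| Fixed 6 | 25.0% | 68.3% |
| Fixed 8 | 20.0% | 66.6% |
| Random 4, 6 | 5.5% | 69.1% |
| Random 2, 4, 6 | 4.1% | 70.2% |
| Random 4, 6, 8 | 2.2% | 67.9% |

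With random 4, 6 and 8, about 0.022 × 86 ≈ 2 patients would have a certain assignment, against 28. Varying the size removes certainty; it hardly reduces informed guessing.

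**Surgical site.** Section 5.1 reports arm surgery in 21 of 43 (parecoxib plus ropivacaine) and 31 of 43 (ropivacaine alone), with two sites missing in the first group. Table 5.5 gives p = 0.102 for site. Among known sites the comparison is 21/41 (51%) with 31/43 (72%), Fisher p = 0.07; it is 0.046 only if the two missing sites are counted as not arm.

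**The case against.** The strongest reply is that two conditions are needed and neither is shown: the operator must have known the block size during recruitment, and must have been able to affect enrolment. An independent statistician generated and alone held the list, and each assignment was disclosed only after recruitment. Sections 4.5 and 4.7 put all eligible patients in the frame and define the subjects as all who were eligible and consented. Section 4.3 gives 393 upper-limb cases a year, which at an even flow is 393 × 70/365 ≈ 75 over the 70 days of recruitment, fewer than the 86 enrolled. On that figure there was little room to pass patients over.

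Most of this stands, and it makes the point conditional. It does not remove it. Section 4.6 itself says potential subjects were sufficient, and the order in which patients enter can matter even when few are skipped. The operator is the primary investigator, for whom knowledge of the design cannot simply be ruled out.

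Two stronger readings are tempting, and the documents support neither.

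- A reader might infer that the block size was public while patients were being enrolled. The only document that gives it is dated 30 November 2017, and recruitment closed on 28 August 2017 (section 4.2).
- A reader might take the surgical-site difference as a trace of selection. It is one variable, split after the fact, and compatible with chance. Age (p = 0.455), weight (0.399), gender (0.382), ASA grade (0.763) and ethnicity (1.000) show no significant difference in Tables 5.4 and 5.5. These comparisons neither show selection nor exclude it.

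**Conclusion.** The point holds as a conditional vulnerability. Given an operator who knew the block size and could influence who entered or when, one third of assignments in full blocks were certain in advance: an expected 28 of 86, with a best-guess rate of about 70.5%. Both conditions are assumptions that the documents leave open. Custody of the list by the statistician does not block this route, so section 4.10.1 claims more than its safeguards can deliver. It should not be read as saying that 28 allocations were in fact foreseen, or that the reported results are biased.

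**What to change.** **For a further trial of this design.** Generate the list with block sizes chosen at random (for example 4, 6 and 8) and withhold them from the operator. Keep the operator out of screening and consent where existing staff allow. Both parts are needed, because varied sizes cut certain assignments to about 2% even if the set of sizes is known but leave the guess rate near 68–70%. The cost is a small change to the randomisation program and a possible final imbalance of a few patients (at most 8/2 = 4 if the last block is incomplete).

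**For this completed trial.**

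1. State who screened and obtained consent, and whether the operator knew the block size during recruitment.
2. From the existing list, mark each assignment as predictable or not (position 4 always; position 3 when the first two were alike). As a sensitivity check, compare baseline factors and the arm differences in block duration between the two sets. With about 28 predictable assignments, this is descriptive and has little power.
3. Reword section 4.10.1 to say that the list was concealed, without claiming that selection bias was prevented, and add predictability to the limitations in section 6.4.

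This needs no new data beyond the list and the enrolment records.

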4.10.2 Details of the administered interventions

The premedication was first prescribed in the morning of the surgery. Upon arrival in the OT, all patients were monitored based on the standard anaesthesia monitoring and for relevant clinical parameters (baseline blood pressure (BP), saturation pressure of oxygen (spO₂), electrocardiography (ECG) and heart rate (HR)) which were obtained using the electric B30 monitor (Stimuplex D® plus 50mm, B. Braun, Melsungen, Germany) and documented before the BPB commenced. Subsequently, IV access of at least 20 G size was inserted on the selected hand of study participants.

Intravenous (IV) loading of Ringer's Lactate solution (B. Braun, Melsungen, Germany) 10 ml/kg was administered before performing the block. Brachial plexus block (BPB) was performed in the block corner at the recovery bay. Drugs regime and other standard equipment for BPB was prepared and acquired and these include:

- 5 mls of Lignocaine 2% for skin infiltration
- 20 mls of Ropivacaine (Naropin®, Astrazeneca) 0.75% + 20mg
 Parecoxib (Dynastat®, Pfizer)(1 mls) ---Group A

- 20mls Ropivacaine 0.75% + 1 ml Normal Saline----Group B.
- Ultra Sonographic machine (Mindray® Version M5, Mindray, Shenzen, China) with high frequency (10-15MHz) linear probe
- 50 to 80mm 22 G insulated peripheral nerve block needle. Vygon,
 France
- o 2% chlorhexidine in 70% isopropyl alcohol solution for skin cleaning

The BPB was implemented by a single operator and assessed by the independent 2nd medical officer in-charge who was blinded and oblivious to the treatment administered. No peripheral nerve stimulator was employed during the procedure. The detailed descriptions of the techniques utilized in the BPB are as follows:

- The block site will be cleaned and draped. The US probe also was draped for the procedure as well.
- SCB technique:
 - Subjects were positioned semi-recumbent with the head turned to the contralateral side with the ipsilateral shoulder slightly elevated with the pillow.
 - An exploratory scan was performed in all patients before the block, by positioning the probe on a coronal oblique plane above the clavicle.
 - Hypoechoic and pulsating supraclavicular artery was then identified, which was lying above the hyper echoic first rib. While maintaining the view of the artery, the probe was then angled until both the first rib and the pleura were also seen simultaneously.
 - After skin preparation and draping, the probe was next placed in the supraclavicular fossa and subcutaneous infiltration will be given on the targeted needle side

- The needle was then inserted from lateral to medial direction in the long axis of the transducer (in-plane technique).
- Nineteen (19) ml of 0.75% ropivacaine and 1 ml of 20 mg of parecoxib
 (Group I: parecoxib + ropivacaine) or 19 mls of 0.75% alone plus 1 ml of
 normal saline (Group II: ropivacaine alone) was then injected at the
 "corner pocket". Adrenaline was not added into any solution.
- The remaining 5 ml was later injected to a point approximately level with the superior/ cephalad aspect of the subclavian artery, but no further than 1 cm lateral to the artery

Block performance-related pain was then evaluated immediately after removing the needle by asking the patient to verbally quantify the level of pain using a score between 0 to 10 (0 meaning no pain, 10 meaning excruciating pain). The study participants were withdrawn from the trial and rescue medications were given if one of the following withdrawal criteria occurred:

- Patient developed local anaesthetic toxicity (seizure)
- Patient developed hemodynamically instability bradycardia/hypotension)
- Patient developed anaphylaxis

The procedures for the assessment of sensory and motor block are as follows:

- Assessment of sensory block:
 - Sensory blockade was assessed every 5 minutes up to 30 minutes following the completion of administration of intervention.
 - Sensory loss was confirmed by the loss to cold sensation using 10 mls cold saline bottle and pinprick sensation using 23G needle in all dermatomes supplied by the brachial plexus (C5-T1).
 - Time zero was defined as the time at which LA was completely injected.

- Sensory block success was defined as complete pin-prick sensory blockade (grade II based on the grading scale employed by Crews *et al.* (2002)) in all dermatomes of the brachial plexus (C5-T1).
- The block was considered incomplete if any supplemental local anesthetic is needed for complete anesthesia.
- The block was considered failed if the desired volume did not provide complete anesthesia or conversion to general anaesthesia was required prior to surgery.
- General anaesthesia was routinely performed with intravenous induction (sedation) agent, short acting opiods and muscle relaxant
- Assessment of motor block:
 - Motor blockade was also evaluated every 5 minutes up to 30 minutes following the completion of administration of intervention.
 - Motor block was assessed by subject's capability of flexing his / her elbow and hand against gravity. This was then graded according to the scale utilised by Borgeat, Ekatodramis and Durmont (2001).
 - Motor block success was considered achieved when the motor power was reduced to grade 3 or more based on the criteria used by Ammar and Mahmoud (2012).
- Intra-surgical assessment:
 - Requirement of block supplementation, surgical wound infiltration and patient requested sedation or general anaesthesia
 - Surgical anaesthesia success was defined as surgery without the requirements of block supplementation, general anesthesia (administered for incomplete block) or surgical site infiltration

- Haemodynamic monitoring was performed at baseline, after LA injection, after 15 min, 30 min, 1 hour of block procedure & after completing surgery.
- Postoperative assessment:
 - Sensory and motor blockade durations were assessed on half-hourly basis (up to 12 hours postoperatively), during the post surgical period.
 - Patient-controlled analgesia (PCA) morphine or IV tramadol was given as rescue analgesia.
 - Pain scores were assessed using the visual rating scale (VRS) (0-10) where pain was evaluated when the patients were resting at 1, 2, 4, 12, 24 hours postoperatively.
 - The duration of analgesia (time interval from the completion of local anesthetic administration until the first need of rescue analgesia in the form of PCA morphine or IV tramadol) and the amount of morphine or tramadol consumed during the postoperative 24 hours were also documented.
 - Any evidence of complications (e.g., bruises/swelling at the block site, chest pain/ breathing difficulty, dysaesthesia/ muscle weakness in the operated extremity not related to the site of operation) were also recorded.
 - Surgeons were alerted to report any neurological problems not related to surgery during the clinical rounds prior to the patients were discharged from the hospital.
 - Anaesthetic preferences (one of the following: 1) the BPB; 2) block under deep sedation; 3) block under GA).
 - Preferred block for future hand operations was then recorded.

4.11 SAMPLE SIZE DETERMINATION

Sample size calculation was performed using Power & Sample Size (PS®) software version 3.1.2 (Dupont and Palmer, Vanderbilt, Nashville, Tenessee, 2014) based on the following outcome parameters:

i) Motor Block Duration –based on Liu et.al, 2013

We are planning a study of a continuous response variable from independent control and experimental subjects with 1 control per experimental subject. In a previous study the response within each subject group was normally distributed with a standard deviation of 139 minutes (Liu *et al.* 2013). If the true difference in the experimental and control means of motor block time is 138 minutes and assuming the attrition (drop-out) rate was 20%, 44 subjects (22 in each intervention arm) were required to reject the null hypothesis that the population means of the experimental and control groups are equal. The type I (α) and type II (β) were fixed at 0.05 and 0.1, respectively and hence the power (1- β) of the study is 0.9.

ii) Sensory Block Duration - based on Liu et.al, 2013

We are planing a study of a continuous response variable from that required 1 control per experimental subject (1:1 control-to-experimental unit ratio). In a previous study, the response within each subject group was normally distributed with standard deviation of 140 minutes (Liu *et al.* 2013). If the true difference in the experimental and control means of sensory block time is 104 minutes and assuming the attrition (drop-out) rate is 20%, we required 39 experimental subjects and 39 control subjects to be able to reject the null hypothesis that the population means of the experimental and control groups are equal with probability (power, $1 - \beta$) of 0.9.The type 1 error probability (α) associated with this test of this null hypothesis is 0.05.

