3.4 RESEARCH HYPOTHESES

- Null hypothesis (H₀): There is no significant difference in the onset of the sensory block is faster in 20mg of parecoxib in 0.75% ropivacaine in comparison to plain 0.75% ropivacaine.
- Null hypothesis (H₀): There is no significant difference in the onset of the motor block is faster in 20mg of parecoxib in 0.75% ropivacaine in comparison to plain 0.75% ropivacaine.
- Null hypothesis (H₀): There are no significant differences in the degrees of sensory and motor block after 30 min is higher in 20mg of parecoxib in 0.75% ropivacaine in comparison to plain 0.75% ropivacaine
- Null hypothesis (H₀): There is no significant difference in the duration of the sensory block in 20mg of parecoxib in 0.75% ropivacaine in comparison to plain 0.75% ropivacaine
- Null hypothesis (H₀): There is no significant difference in the duration of the motor block in 20mg of parecoxib in 0.75% ropivacaine in comparison to plain 0.75% ropivacaine.

SECTION 4

RESEARCH METHODOLOGY

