5.1 THE CLINICO-DEMOGRAPHIC PROFILES OF THE STUDY PARTICIPANTS

[figure not shown]
On the whole, 86 study participants were included in the analysis. The mean age and weight of the participants are similar between the two groups of interventions. Apart from that, both intervention groups exhibit similar patterns of VRS pain score, volumes of local anaesthetics received, supplemental local anaesthetics received and PCA morphine profiles.

With regards to gender and ethnic compositions, both intervention groups, in general, demonstrated similar proportions of females, males and each ethnic groups. Furthermore, both intervention arms have also relatively the same proportions of participants for each ASA grade. Nevertheless, with respect to the specific surgical sites, more study participants in the ropivacaine group had surgeries to their arms whilst more patients in the combined parecoxib-and-ropivacaine group had surgeries to their forearms. Besides, there are also two missing data in this group. However, it can be safely said that proportions of surgical sites are roughly similar in both groups. For further information, refer to table 5.1 and figures 5.1-5.3.

Parameters 1	Parecoxib + Ropi Mean (SD)	vacaine (n=43) n(%)	Ropiva Mean (SD)	caine (n=43) n(%)
Age	43.8 (13.7) 47.5 (26) ^a		46.3 (12.6) 51.0 (21.0) ^a	
Weight (kg)	60.8 (7.6) 60.0 (13.0) ^a		61.6 (7.6) 60.0 (12.0) ^a	
VRS pain score	1.0 (0)		1.0 (0)	
LA volume	20.0 (0)		20.0 (0)	
Supplement LA volume	0.0 (0)		0.0 (0)	
Time to 1 st PCA morphine (hours)	0.0 (0)		0.0 (0)	
PCA Morphine deman within 24 hours (count			0.0 (0)	
PCA Morphine given within 24 hours (count	0.0 (0) s)		0.0 (0)	
Gender Female Male		16 (37.2) 27 (62.8)		0 (46.5) 3 (53.5)
Ethnicity				
Malay Chinese Others		42 (97.7) 1 (2.3) 0 (0)	۷	41 (95.3) 1 (2.35) 1 (2.35)
Surgical sites Forearm Arm Hand Fingers Missing		14 (32.5) 21 (48.9) 0 (0) 6 (14.0) 2 (4.6)		$\begin{array}{cccc} 8 & (18.6) \\ 31 & (72.1) \\ 1 & (2.3) \\ 3 & (7.0) \\ 0 & (0) \end{array}$
ASA grades I II		7 (16.3) 36 (83.7)		6 (14.0) 37 (86.0)
Preoperative VRS scor ^a Median (Interquartile range			0.0 (0.0)	

Table 5.1: The clinico-demographic characteristics of study participants (n = 86)

^aMedian (Interquartile range)

[figure not shown]

Figure 5.1 (a-b): The proportions and percentages of subjects in each intervention arm, as stratified by gender and ethnicity of subjects

[figure not shown]

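### Section 4.11 claims 90% power with 20% attrition allowed for, but for a two-sided 0.05 test 22 and 39 per arm are evaluable numbers; after 20% loss from 39, sensory power is about 82%

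*Combined protocol and SAP*

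**What the plan says.** Section 4.11 bases two calculations on an earlier axillary-block trial.

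- **Motor duration:** difference 138 minutes, SD 139 minutes; "assuming the attrition (drop-out) rate was 20%, 44 subjects (22 in each intervention arm) were required to reject the null hypothesis". The error rates are given as "The type I (α) and type II (β) were fixed at 0.05 and 0.1, respectively", which makes the stated power 0.9.
- **Sensory duration:** difference 104 minutes, SD 140 minutes, power 0.9; "assuming the attrition (drop-out) rate is 20%, we required 39 experimental subjects and 39 control subjects". The section adds: "The type 1 error probability (α) associated with this test of this null hypothesis is 0.05".

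The number of sides is not stated, and no pair of figures before and after attrition is given. Sensory duration needs the larger number, so it sets the trial size: 2 × 39 = 78.

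In section 3.4 the null hypothesis for sensory duration has no direction: "There is no significant difference in the duration of the sensory block in 20mg of parecoxib in 0.75% ropivacaine". Section 5.1 reports the number analysed: "On the whole, 86 study participants were included in the analysis", that is 43 per arm.

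**The concern.** If 20% attrition is built in, removing 20% of the printed number should leave enough patients for 90% power. Instead, the printed numbers match the usual two-sided formula with nothing added for attrition.

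Sensory duration is the outcome affected, because it governs the size of the trial. Section 6.4 relies on the calculation when it defends the trial's power, and anyone reusing 4.11 to plan a similar trial with 20% expected loss would enrol too few.

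**Working it through.** **Inputs.** From 4.11: alpha 0.05, power 0.90, 1:1 allocation, 20% attrition, and difference/SD of 138/139 (motor) and 104/140 (sensory) minutes.

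**1. Reproducing the printed sizes.** n per arm = 2(z_α + z_β)²(SD/difference)², with z_β = 1.2816.

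| | Motor | Sensory |
|---|---|---|
| Two-sided (z_α = 1.9600), no attrition | 2 × 10.507 × (139/138)² = 21.32 → **22** | 2 × 10.507 × (140/104)² = 38.08 → **39** |
| Two-sided, noncentral t, no attrition | 22.33 → 23 | 39.07 → 40 |
| One-sided (z_α = 1.6449), no attrition | 17.38 | 31.04 |
| One-sided, divided by 0.8 | 21.72 → **22** | 38.80 → **39** |

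Two routes give 22 and 39: two-sided with no attrition, and one-sided with attrition. The text does not show which was used.

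**2. Which test the trial uses.** The duration null hypotheses in 3.4 have no direction. The printed results are two-sided:

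- Table 5.4, motor onset, U = 900.50, 43 per arm: z = (900.5 − 924.5)/√(43 × 43 × 87/12) = −0.207. Two-sided p is 0.836 and one-sided 0.418, without tie correction; printed 0.832.
- Table 5.4, sensory onset, U = 861: 0.583 two-sided, 0.292 one-sided; printed 0.577.
- Table 5.5, 43/0 against 42/1, Fisher's exact test: 1.000 two-sided, 0.5 one-sided; printed 1.000.

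**3. Two-sided power on the planning inputs (noncentral t).**

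| Situation | Evaluable per arm | Power |
|---|---|---|
| Sensory, 39 per arm, no loss | 39 | 89.95% |
| Sensory, 39 per arm, 20% lost | 31 (31.2 before rounding) | 82.1% (83.3% at 32) |
| Motor taken alone, 22 per arm, no loss | 22 | 89.6% |
| Motor taken alone, 22 per arm, 20% lost | 17–18 | 80–82% |
| Motor at the governing 39 per arm, 20% lost | 31 | 97.0% |
| Sensory, 43 per arm, no loss | 43 | 92.6% |
| Sensory, 43 per arm, 10% lost | 38.7 | 89.7% |
| Sensory, 43 per arm, 20% lost | 34–34.4 | about 86% |
| Motor, 43 per arm, 20% lost | 34 | 98.1% |

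The normal approximation gives 83.3% for sensory duration at 31 per arm, so the choice of method moves the key figure by about one point.

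**4. Sizes that do allow for 20% attrition (two-sided, n/0.8).**

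- Motor: 21.32/0.8 = 26.65; 22/0.8 = 27.5; 22.33/0.8 = 27.9; 23/0.8 = 28.75. Rounded up, 27–29 per arm.
- Sensory: 38.08/0.8 = 47.6; 39/0.8 = 48.75; 39.07/0.8 = 48.8; 40/0.8 = 50. Rounded up, 48–50 per arm.

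**5. Number analysed.** With SDs 0.77 and 0.60 and 43 per arm, the Welch degrees of freedom are 42 × (0.5929 + 0.36)²/(0.5929² + 0.36²) = 79.3, against 79.342 in Table 5.4. This agrees with 43 analysed per arm.

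**The case against.** The strongest reply is that a one-sided 0.05 calculation with attrition also gives 22 and 39, so the authors may have included the allowance. The p-values show how the data were tested, not what was entered in the software, and the onset and degree hypotheses in 3.4 contain directional words. That stands as far as the origin of the figures goes. It does not rescue the claim: a one-sided plan does not match non-directional duration hypotheses and two-sided p-values, and sensory power for a two-sided test after 20% loss is still about 82%.

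Other points have some force:

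- **Model.** Sensory duration was finally compared by Mann-Whitney, whereas these are t-test powers. They follow the model in 4.11, which assumes normality and compares means, so they are planning figures.
- **Inflation rule.** 4.11 names none. Multiplying by 1.2 in the normal formula gives 26–27 and 46–47 per arm. These still exceed the printed sizes, and 0.8 × 47 = 37.6 falls short of the 38.08 evaluable needed.
- **Origin of 86.** The flow chart was not available to this review, so the safe statement is that 4.11 does not explain it. A 10% margin is possible (39 × 1.1 = 42.9 → 43), but that is inference.
- **Consequence.** The trial is complete, 86 were analysed, and both durations were reported with p < 0.001. The practical effect is therefore small.

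**Conclusion.** The concern holds. For a two-sided 0.05 test, 90% power after 20% attrition is not delivered by 39 per arm for sensory duration (about 82%), nor by 22 per arm for motor duration taken alone (80–82%). In the trial as sized, only sensory duration falls short; motor power at 39 per arm remains about 97% after the same loss.

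This rests on the differences and SDs in 4.11, a t-test comparison of means, and a single test at 0.05 with no adjustment for the interim analyses or the several end-points. It corrects a stated figure. On the planning inputs, the at-least-90% statement in 6.4 is met at the 43 per arm analysed (92.6%), provided there is no appreciable loss.

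**What to change.** In section 4.11:

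1. State that alpha is two-sided.
2. With that stated, describe 22 (motor) and 39 (sensory) per arm as evaluable numbers before attrition. If the original calculation was one-sided, say so and replace it with the two-sided one.
3. Give the sizes that allow for 20% attrition, 27–29 (motor) and 48–50 (sensory) per arm, naming the formula and rounding used.
4. Explain how 86 was reached from 78, and give its sensory power: about 93% with no loss, about 90% with 10% loss and about 86% with 20% loss.

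In section 6.4, add a short note that the 90% statement depends on there being no appreciable loss.

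The cost is wording only: no additional patients and no re-analysis.
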